1. TITLE

A randomized comparison of early deployment of a video capsule (Endocapsule EC-10: Olympus Tokyo, Japan) in Clinical Decision Unit (CDU) versus standard of care (SOC) work-up of hematemesis [H] and non-hematemesis gastrointestinal bleeding [NHGIB].

2. EXTERNAL IRB REVIEW HISTORY*

Not applicable.

3. PRIOR APPROVALS:

This is an inter-departmental study with the Emergency Department and Division of Gastroenterology. [name] and [name] are the principal investigators.

Conflict of Interest (COI):

PI has discussed the project with [name], chair of the COI committee. Neither investigator has any financial conflicts of interest.

Clinical Engineering Department:

The project will require placement of a computer workstation on wheels (WOW) in the CDU and another in the GI Research Office. These, as well three recorder systems, will be installed with the help of the clinical engineering department and cleared by them prior to use.

Biohazardous Agents:

Not applicable.

Radiation:

The 'Questions for PI Checklist' from the Subcommittee on Human Uses [SHU] of the Radiation Safety Committee [RSC] has been reviewed and there is no requirement for pre-approval by the subcommittee. A copy of this checklist has been added to attachments. A KUB is only performed on those patients whose capsule does not reach the cecum before the battery runs out and who do not see the capsule excreted in their feces in the 2 weeks following the procedure. This is standard of care.

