All medications in the study, erythromycin and metoclopramide and those used for conscious sedation during endoscopy are FDA approved

All procedures in the study are used in a conventional manner and are devices are all FDA approved. Risks of endoscopy include sore throat, bleeding, perforation and infection. Conscious sedation risks are hematoma during placement of an IV, over sedation, aspiration and pneumonia.

Procedures

INVESTIGATOR STUDY PLAN - H00015196

Capsules are swallowed with a small [4-12 oz.] amount of water. As noted above, patients will not have the capsule deployed until it has been confirmed that 10 hours have passed since the patient had last eaten. Patients are allowed to take medications up to two hours prior to ingesting the capsule (which is standard of care).

Immediately following ingestion of the VCE a research staff member will use the capsule's Real-Time Viewer (RTV) to inspect for blood in the stomach. If blood is found in the stomach, the recording will be stopped. At 40-60 minutes following VCE

INVESTIGATOR STUDY PLAN - H00015196

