ingestion, a staff member will again use the RTV to confirm that the capsule has entered the small bowel. If the capsule at that time is still in the stomach a prokinetic agent (either metoclopramide or erythromycin, [these agents are commonly used in patients with upper GI bleeding to help get blood clot out of the stomach prior to upper endoscopy to help clear the stomach to improve the chance of finding the source of bleeding]. Based on experience the need for either prokinetic agent is in approximately 1 out of 8 patients. If a prokinetic agent is required a staff member will check within another 40-60 minutes to again verify that the capsule has moved to the small intestine. No further prokinetic will be given. For the H group the recording will be stopped after the small bowel has been entered. For the NHGIB group four to 5 hours after ingestion, a staff member will use the RTV to again check for blood. This is the mean small intestinal transit time of the small intestine. If the VCE is in the cecum, the recording will be stopped and data will be downloaded to the workstation and processed into a video. If the VCE has not reached the cecum, at four and eight hours after ingestion, a staff member will again check the RTV to see if blood is present and/or the ileocecal valve has been passed. Data from the capsule recorder will be downloaded to a workstation as soon as possible. Battery life for the EC-10 capsule is now >12 and up to 20 hours

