During hospitalization, data will be recorded from ED pulse check, and EPIC regarding fluid administration, transfusion of pRBC, initial hematocrit, times and types of procedures (e.g. upper endoscopy, enteroscopy, colonoscopy etc), time from entry to ED and CDU, to time to localization of source of bleeding, admission disposition discharge from CDU, regular floor, ICU), time of discharge. The procedures involved in the hospitalization (i.e. upper endoscopy, enteroscopy, and colonoscopy) will be done as part of standard of care. All of this information will be linked to the subject's study ID number as described above. This data collection is for research purposes only.

In addition, the costs of the procedures will be collected through financial services. The costs that will be collected are both the fixed and variable costs associated with each patient in the study. We will also collect the direct and indirect costs allocated to each patient. All charges associated with the admission for each patient in the study will have costs allocated. This will be evaluated as an additional data point to compare the two arms of the study. No additional PHI will be collected.

Telephone Follow-Up

Those subjects discharged from the CDU will be contacted the following day by phone by a research staff member to make sure that they are doing well and that the appropriate follow up procedure has been arranged. Each patient will be called 30 days after discharge to check to see if bleeding has recurred. Please see attached form for telephone script that staff member will read along with particular questions that will be asked.

No more than three attempts will be made at each time point to reach the subject. If a message is left, it will be "Hello, this is [name] calling from UMass looking to speak with [subject]. Please call back at [number] at your earliest convenience. Thank you."

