16. RISKS TO SUBJECTS*

This study is investigating the benefits of re-ordering the process of the current care algorithm for H and NHGIB. Video capsule endoscopy is already part of standard of care for many GI bleeding workups. This is not a new diagnostic modality and no new risk is being introduced from this technology itself. There are no anticipated risks to subjects who are randomized to the early deployment of the capsule and the detection of active bleeding is expected to be at least comparable to the standard deployment.

One anticipated risk is a breach of confidentiality and to minimize this risk all identifiers will be destroyed. In order to minimize this risk, as described in Question 13, identifiers will be destroyed. Data collected will be analyzed using study ID numbers only.

The most significant risk of VCE is capsule retention. This risk is the same for both groups and there is no anticipated unforeseen risk with early deployment. The risks do not change based on timing. Capsule retention is when the video capsule does not complete its transit throughout the GI tract. Studies have varied in their reports of the frequency of capsule retention with rates of about 1%, ranging from 1-13% of total cases. The latter figure is for a study on Crohn's disease patients. If capsule retention occurs, subjects may require radiologic imaging. This usually consists of a plain film of the abdomen taken 2 weeks after the capsule was swallowed to localize the capsule. They will not be kept in hospital for this. If the patient sees the capsule in their feces, this test is not needed. The recently extended battery life of the capsule almost eliminates incomplete transit. If there is long term retention then this is likely to provide information on a previously undetected health issue that the patient has and this will be managed as is required.

Removal of a capsule may be achieved by deep enteroscopy or at the time of surgery which is usually performed to remove the cause of the retention e.g. a tumor or stricture. The capsules may be left in place, Patients have been known to safely retain the capsule for years without ill effects.

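### The abdominal-film rule in Section 3 turns on cecal arrival, which is not recorded when the recording is deliberately stopped early, and Section 16 describes the film on a different basis

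*Protocol*

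**What the plan says.** Protocol Section 3, under Radiation, sets two conditions for the film, joined by an and. The first is: "A KUB is only performed on those patients whose capsule does not reach the cecum before the battery runs out". The second follows in the same sentence: "and who do not see the capsule excreted in their feces in the 2 weeks following the procedure".

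Section 11 (Procedures) ends some recordings well before the cecum. For hematemesis: "For the H group the recording will be stopped after the small bowel has been entered". For any patient: "If blood is found in the stomach, the recording will be stopped".

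Section 16 describes imaging for retention without mentioning the cecum or the battery: "This usually consists of a plain film of the abdomen taken 2 weeks after the capsule was swallowed to localize the capsule". It waives the film if the patient sees the capsule in the stool. Section 28 defines true retention as lasting more than 2 weeks, again with no condition on the recording.

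Section 11 describes two telephone contacts. Patients discharged from the CDU are called the next day about how they are and whether follow-up is arranged. For everyone: "Each patient will be called 30 days after discharge to check to see if bleeding has recurred". The script is an attachment and was not available. Section 14 says in general terms that subjects will be followed for complications of capsule endoscopy throughout participation.

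**The concern.** Section 3 uses the word only, so it reads as a restriction: no film unless both conditions hold. Where the recording has been stopped on purpose, nobody observes whether the capsule reached the cecum before the battery ran out. Staff following Section 3 could then reasonably decide either way about a patient who has not seen the capsule pass, while Section 16 points to a film.

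Section 16 ranks retention as the leading risk of the capsule, and Section 10 makes complication rates a secondary endpoint. Every early-capsule patient swallows a capsule, whereas Section 11 expects only a few standard-of-care patients to do so. Any incomplete ascertainment of retention would therefore fall mostly on one arm. Section 11 also expects most capsules to pass at 24 to 72 hours, and CDU observation lasts up to 23 or 24 hours (Sections 11 and 29). For patients discharged from the CDU, passage will often happen at home, where the study learns of it only by asking.

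**Working it through.** The plan gives no figure of its own to reproduce here. The check is one of logic, with a small calculation for scale.

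**Can the first condition be observed?** Times are minutes after ingestion, from Section 11.
- First check of small-bowel entry: "At 40-60 minutes following VCE" ingestion, so 40 to 60.
- Second check, if needed: "If a prokinetic agent is required a staff member will check within another 40-60 minutes", so 40 + 40 = 80 to 60 + 60 = 120.
- First later check that could show the cecum, described for NHGIB only: 4 to 5 hours, so 240 to 300.
- Battery life: more than 12 and up to 20 hours, so more than 720 and up to 1200.

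An H recording that ends at small-bowel entry therefore stops at about 40 to 120 minutes, far short of the cecal check and of battery exhaustion. A recording stopped for gastric blood ends with the capsule still in the stomach. (Section 11 does not say when an H recording ends if the capsule is still in the stomach at the second check.)

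**To whom does this apply?** Planned early-capsule patients: 40 H + 40 NHGIB = 80. The H stopping rule covers 40/80 = 50% of them. NHGIB patients with gastric blood add a number that the documents do not give.

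**What does each section say about a patient whose recording was stopped?**
- Capsule seen within 2 weeks: Section 3 gives no film, because its second condition fails. Section 16 gives no film. They agree.
- Capsule not seen, and an unrecorded cecum is taken as not reached: Section 3 permits the film. This agrees with Section 16.
- Capsule not seen, and an unrecorded cecum is taken as the first condition not being shown: Section 3 rules the film out. This conflicts with Section 16.

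The protocol does not choose between the last two readings. The conflict is thus confined to patients with a stopped recording who do not see the capsule pass.

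**How often might retention occur?** Section 16 gives a rate of about 1%. With n = 40 H capsules and p = 0.01:
- Expected retentions: n × p = 40 × 0.01 = 0.4.
- Chance of at least one: 1 − (1 − p)^n = 1 − 0.99^40 = 0.331, or 33%.

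This is the chance that retention happens. The chance that it is missed is smaller and cannot be computed, because it depends on how many patients fail to see the capsule and on how staff read Section 3.

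**The case against.** The strongest reply is that the protocol, read as a whole, already has a workable rule. Section 3 is a note on radiation approval, not the procedures or safety section. Section 16 gives a test based on excretion that can be applied to any patient, and Section 28 defines retention by time alone. Section 3 can be read to agree with them. Section 14 promises follow-up for capsule complications throughout participation, which Section 9 puts at about 31 to 40 days and so spans the 2-week point. The 30-day call falls after the 2-week threshold and could establish passage, and the unseen script may already ask.

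Much of this stands. A reader might infer that retention cannot be judged at all in patients whose recording was stopped. The documents do not support that: a patient who sees the capsule pass needs no cecal information, and Section 16 offers a usable test for the rest. Nor does the absence of a call at exactly 2 weeks prevent retentions from being counted.

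A reader might also take larger figures from the protocol. The upper retention rate of 13% would give 40 × 0.13 = 5.2 retentions, but Section 16 attributes it to Crohn's disease patients, and Section 6 excludes inflammatory bowel disease. Using all 80 capsule patients gives 1 − 0.99^80 = 0.552, but that includes NHGIB patients whose cecal arrival is checked.

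What the reply does not remove is the conflict itself. Section 3 says only, and does not classify a recording stopped by design. Section 16 opens by supposing that retention has occurred, and does not acknowledge the Section 3 restriction. The general statement in Section 14 does not say which rule governs.

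**Conclusion.** The point holds as an inconsistency in a stated safety rule, not as a demonstrated failure to detect retention. One condition of the Section 3 rule goes unrecorded by design under the H stopping rule, which covers half of the planned early-capsule patients, and in an unstated number of NHGIB patients. The sections conflict for those among them who do not see the capsule pass.

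The expected scale is small: 0.4 retentions among 40 H patients, assuming the 1% rate applies and that patients are independent. At that frequency a material bias in the complication-rate comparison is not shown. The primary endpoint, sample size and error rate are untouched. The point still deserves action, because it concerns the protocol's own leading device risk and costs little to settle. The part about telephone contacts is conditional: the calls as described are not stated to ask about capsule passage, but the script could show that they do.

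**What to change.** 1. Reconcile Sections 3, 11 and 16 so that they say the same thing about a patient whose recording was deliberately stopped before the cecum. What should prompt a film is a clinical decision for the investigators.
2. If the telephone script does not already do so, ask about capsule passage at an existing follow-up call.
3. Record capsule status as passed, retained or unknown for every patient who swallowed a capsule, in either arm.
4. Report capsule complications with the number of unknowns beside them, so that an unknown is not counted as free of retention.

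The cost is some protocol wording, at most one script question, one data field, and possibly a few additional films of a kind that Section 16 already describes as usual.

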4. OBJECTIVES*

- 1) The objectives of this study are to compare the efficacy of video capsule endoscopy (VCE) as first line vs the standard of care workup of H [upper endoscopy] and NHGIB by endoscopy [upper, lower and other tests] in the rate of detection of active bleeding in patients admitted to the clinical decision unit (CDU). We propose to examine differences in time to detection of active bleeding, diagnosis, reduction in numbers of procedures, hospital costs and length of stay between a conventional workup protocol and our proposed protocol of early capsule endoscopy deployment. All patients in the SOC group will be admitted to the

INVESTIGATOR STUDY PLAN - H00015196

hospital. These will be compared to those in the VCE first group who are stable and may be discharged from the CDU directly.

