The PI or sub-investigator will then view the video of the capsule recording [it takes about 5 minutes to establish if there is bleeding and where it is coming from. More detailed analysis will take about 15-20 minutes]. As soon as the capsule recording has been reviewed, the PI or sub-investigator will inform the patient's attending gastroenterologist on the consult service as to where the bleeding is coming from or that bleeding is not seen, as soon as possible after the video has been reviewed. Depending on the findings a recommendation will be made as to the next most appropriate test. See attached Figure 1. If blood is found in the esophagus, stomach or duodenum an upper endoscopy is recommended. If blood is seen in the small intestine, it will be recommended that the subject next have a push enteroscopy, deep enteroscopy, or angiography. If blood is found in the right colon, colonoscopy may be performed or deferred to colonoscopy as an outpatient, if active bleeding has ceased. If the capsule study is not diagnostic and no blood is seen in the GI tract and there is no ongoing hematochezia, the subject will be placed in ED observation for up to 23 hours and evaluated for potential discharge and follow-up by gastroenterology as an outpatient. If, and as appropriate an EGD or colonoscopy will be performed as an outpatient within 72 hours.

For most subjects, the capsule will pass in a bowel movement within 24 -72 hours of ingestion.

An equal number of subjects [up to 40] will be randomized to the "SOC group." For NHGIB workup may include upper endoscopy, colonoscopy, and additional capsule or small bowel enteroscopy depending on the subject's presentation and the results of the workup performed by the gastroenterology team. For some subjects, the VCE would be done as part of standard of care. We estimate that 4-10% of patients will have small intestinal bleeding. For patients requiring a video capsule endoscopy as part of "SOC workup" the patients will be given the same Olympus video capsule that is used in the "Early Capsule" group. Further management would be as standard of care which requires

INVESTIGATOR STUDY PLAN - H00015196

admission. These subjects will be discharged on the recommendation of the attending hospitalist after completion of treatment.

Review and Follow-Up

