It is not expected that there is any risk that the subjects assigned to the early capsule group will require more diagnostic procedures than the conventional work-up group. The hypothesis of this study is that the early deployment group may, in fact, undergo fewer procedures and have a shorter hospitalization compared to those having a conventional work-up.

Another potential risk to the subjects in the study relates to the prokinetic medications (metoclopramide and erythromycin) which would be given if the capsule is slow to leave the stomach. Risks associated with the use of metoclopramide include allergic reactions (e.g., skin rash or difficulty breathing), extrapyramidal reactions, central nervous system effects (e.g. insomnia, headache, confusion), neuroleptic malignant syndrome, endocrine disturbances (e.g. galactorrhea, amenorrhea, gynecomastia), and cardiovascular effects (e.g. hypotension, tachycardia, bradycardia, heart failure, and AV block). The adverse effects of metoclopramide are directly correlated to the duration and dose of the drug given, so we expect the incidence of adverse effects to be minimal, given that we are giving one dose only for the purpose of this study. For erythromycin, adverse effects

INVESTIGATOR STUDY PLAN - H00015196

include allergic reactions (e.g., skin rash or difficulty breathing), gastrointestinal effects (including nausea, vomiting, abdominal pain, diarrhea, and anorexia), hepatic dysfunction, pseudomembranous colitis, QT prolongation, and ventricular tachycardia.

These drugs are frequently used in patients with upper GI bleeding to help empty the stomach of clot prior to endoscopy to enhance visualization of the bleeding site(s). Single doses of these drugs have very low risk.

Risks of endoscopy are of bleeding, perforation and infection. Risks of conscious sedation in these patients is hypoxia, aspiration, pneumonia and very rarely death. None of the procedures used in the trial are outside the stand of care for gastrointestinal bleeding.

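### Read literally, the last sentence of Section 4 compares all SOC patients with a post-randomisation subset of the capsule arm; this conflicts with the whole-arm comparison described elsewhere, and no defined analysis population settles it

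*Protocol*

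**What the plan says.** Protocol Section 4 ends with two linked sentences. The first reads "All patients in the SOC group will be admitted to the" hospital. The second reads "These will be compared to those in the VCE first group who are stable and may be discharged from the CDU directly". The sentence before these two describes a different contrast, for time to detection, procedures, costs and stay: "between a conventional workup protocol and our proposed protocol of early capsule endoscopy deployment".

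Section 11 explains how a capsule patient comes to be considered for direct discharge. If the capsule study is not diagnostic, "no blood is seen in the GI tract and there is no ongoing hematochezia, the subject will be placed in ED observation". This period is limited to 23 hours, and the patient is assessed for possible release home under outpatient GI care. On the SOC side, the same section says "Further management would be as standard of care which requires" admission.

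Other text points to whole arms. On cost, Section 11 says "This will be evaluated as an additional data point to compare the two arms of the study". Section 16 gives the hypothesis that the early deployment group may "undergo fewer procedures and have a shorter hospitalization compared to those having a conventional work-up". Section 13 plans chi-square tests, t-tests and Kaplan-Meier curves on two cohorts, without saying who belongs to each.

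**The concern.** The wording of the last sentence is restrictive: it picks out those capsule patients who meet a condition, and sets them against an SOC group described as all patients. Hemodynamic stability is already an entry criterion for everyone (Section 6). Being dischargeable from the CDU is known only after randomisation, and in the capsule arm it depends largely on the capsule finding.

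An analysis on that basis would drop most capsule patients found to be bleeding while SOC kept all of its own. Randomisation would no longer protect the comparison. Shorter stay, fewer procedures, lower cost and fewer admissions could then appear even if the capsule changed nothing, simply because lower-risk patients were compared with a mixed group. These are secondary endpoints in Section 10, and Section 5 names procedures, admission and stay among the questions the trial is meant to answer.

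**Working it through.** **Who is compared, by section (protocol)**

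| Place | Capsule side | SOC side |
|---|---|---|
| Section 4, last sentence | Stable patients who may leave the CDU directly | All, admitted |
| Section 4, preceding sentence | Early capsule protocol | Conventional protocol |
| Section 5, closing question | Patients with H and NHGIB, no subset | Same |
| Section 11, costs | Arm | Arm |
| Section 13 | Cohort, undefined | Cohort, undefined |

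Neither document states an intention-to-treat principle or defines an analysis set. The document filed as the SAP is a DSMB charter; its Section 9 refers to an SAP to be reviewed before data are first presented. Section 15 of the protocol also removes some patients for reasons that can arise after randomisation, so analysis of everyone randomised cannot simply be presumed.

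**Inputs for an illustration**

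The documents give no figure for this comparison to reproduce, and no length-of-stay data.

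- Patients per arm in each bleeding group: 40 (Sections 11 and 13).
- Dischargeable share q: 30%, from the earlier hematemesis trial cited in Section 5. Applying it to this trial, and to NHGIB in particular, is an assumption. Range shown: 20% to 40%.
- Mean stay of low-risk patients, L: 1 to 2 days (assumed).
- Mean stay of the others, H: 3 to 5 days (assumed).
- No effect of the capsule on stay; the discharged subset is the low-risk group.

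**Length of stay**

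Subset size = 40q = 40 × 0.30 = 12.

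SOC mean = qL + (1 − q)H, and the full capsule arm has the same mean, so the full-arm difference is 0. The subset mean is L. The spurious saving is therefore qL + (1 − q)H − L = (1 − q)(H − L).

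| q | Comparison | L = 2, H = 3 | L = 1, H = 5 |
|---|---|---|---|
| 0.20 | 40 v 8 | 0.8 × 1 = 0.8 days | 0.8 × 4 = 3.2 days |
| 0.30 | 40 v 12 | 0.7 × 1 = 0.7 days | 0.7 × 4 = 2.8 days |
| 0.40 | 40 v 16 | 0.6 × 1 = 0.6 days | 0.6 × 4 = 2.4 days |

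**False-positive rate**

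Simulation of a two-sided 5% t-test with no true effect used lognormal stay (log-SD 0.8), low-risk stay one half or about one third of the others, q = 0.30 and 5,000 runs per scenario. The rejection rate was 4.7% and 4.3% for full arms, and 22% and 46% for the subset comparison.

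**Admission**

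Suppose 12 of 40 capsule patients are discharged and all 40 SOC patients are admitted.

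- Subset comparison: 0/12 v 40/40, or 0% v 100%, by definition.
- Full arms: 28/40 v 40/40, or 70% v 100%.

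Of the 100-point gap in the subset comparison, 30 points would remain with full arms. Those 30 points partly reflect the design, because Sections 4 and 11 fix SOC admission at 100%.

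Procedures and cost were not calculated, because the documents give nothing to calculate from. For them only the direction can be argued.

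**The case against.** The strongest reply is that one loosely worded sentence is being read as an analysis plan. Every capsule patient is stable at consent, and the phrase about discharge can be read as describing a route open to the capsule arm, in contrast to an SOC arm that is admitted. Section 4 assigns no test and no analysis set. The title, the preceding sentence, the closing question of Section 5, the cost paragraph in Section 11 and the allocation of 40 per arm all suggest whole arms. The subset reading also defeats the protocol's own endpoints: admission would be 0% by definition, and time to detection would have almost no events among patients in whom no blood was seen.

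Much of this stands. It makes the whole-arm reading the likelier intention. It does not remove the problem, because the grammar favours the subset and nothing in either document overrides it.

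Three stronger readings are tempting and are not supported.

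- A reader might infer that the trial is committed to a subset analysis, so that its objective cannot be answered. The documents contradict themselves on this; they do not settle on the subset.
- A reader might infer that the subset excludes everyone found bleeding. Section 11 lets colonoscopy be deferred to outpatient care when blood is seen in the right colon and active bleeding has ceased, so some patients with a positive capsule could go home.
- A reader might infer that the whole admission gap is spurious. Part of it follows from the SOC arm being admitted by design and would remain in a full-arm analysis.

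**Conclusion.** The concern holds as an internal contradiction about who is compared. The literal wording selects on a post-randomisation state, and if followed it would favour the capsule on stay, procedures, cost and admission. This assumes that patients fit for direct discharge are at lower risk and stay less.

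The figures are illustrations only. The stated saving of 0.7 to 2.8 days rests on a 30% share borrowed from a hematemesis trial and on assumed stays; shares of 20% to 40% widen it to 0.6 to 3.2 days.

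This should be fixed, but it is not a fatal flaw: the endpoints concerned are secondary, no effect on the primary analysis has been shown, and whole arms are probably what was meant.

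**What to change.** Replace the last sentence of Section 4 with wording such as: *All patients randomised to VCE first will be compared with all patients randomised to SOC, by assigned arm, within the H and NHGIB groups, for every endpoint. Direct discharge from the CDU is an outcome and does not define who is analysed.* Results for CDU-discharged capsule patients can be reported descriptively, without an SOC comparison. Section 13 and the SAP should carry the same definition.

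The statements on SOC admission must also be reconciled. Sections 4 and 11 say SOC patients are admitted, whereas Section 5 allows patients in either group who are not bleeding to go home without admission. Section 29 describes an admit-or-discharge decision for recruited patients generally. The choice bears directly on what the admission, stay and cost contrasts mean.

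The cost is a few sentences, with no new data and no more patients. Reported differences would be expected to be smaller than the subset comparison would show. If whole arms were always intended, nothing is lost.
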